4.4 Definition of Planned versus Actual Treatment

Participants will receive a single IV infusion of **CCI** Lu AG09222, or **CCI** Lu AG09222 or Placebo.

Planned treatment is defined as the treatment a participant was randomized to.

Actual treatment is defined as the treatment a participant actually received during the trial.

For reporting purposes, the following will be summarized by planned treatment:

- Efficacy
- Demographics and baseline characteristics
- Disposition
- eDiary compliance
- Concomitant medication

And the following will be summarized by actual treatment:

- Adverse events
- Exposure
- Immunogenicity
- Laboratory parameters, vital signs, ECG, and C-SSRS

Unless otherwise specified, data listings will display actual treatment.

4.5 Definition of Region

The following countries are included in the regions:

- North America: United States of America
- Europe: Czech Republic, Georgia, Denmark, Slovakia, Poland

4.6 Definitions for CCI [REDACTED] Migraine Day, Headache Day, CCI [REDACTED]

Participants will complete an eDiary, from the Screening Visit until the Safety Follow-up Visit or Efficacy Follow-up/Withdrawal Visit. In the headache diary, participants collect daily information on key symptoms and characteristics as mentioned in the definition of migraine (see section 4.6.2). For each day, the participant will record if they experienced any headaches. For each experienced headache, the start and stop date and time will be collected. The participant will record further daily information regarding headache characteristics (for instance, headache severity, additional symptoms) CCI [REDACTED]. Headache items will be assessed with a yes/no response; and severity will be rated as mild, moderate, or severe. Participants are expected to complete the eDiary on a daily basis during the trial regardless of whether they experienced a headache on that day.

CCI [REDACTED]

The eDiary-reported headache characteristics will be used in derivations of efficacy endpoints, including rules for handling missing data, as described in section 22.1.1.

For the purpose of endpoint derivations, CCI [REDACTED] and migraine and headache days are defined as described below.

4.6.1 CCI [REDACTED]

CCI [REDACTED]

4.6.2 Migraine Day

A migraine day is defined as a day with a headache that meets following criteria listed below:

1. A headache that:

Lasted 4 hours or more and had at least 2 of the following:

1. Unilateral location
2. Pulsating quality
3. Moderate or severe pain intensity
4. Aggravation by or causing avoidance of routine physical activity

and had at least 1 of the following:

1. Nausea and/or vomiting
 2. Photophobia and phonophobia
2. Or A headache that lasted 30 minutes or more and the participant had an aura with the headache (migraine with aura*)
3. Or A headache that lasted 30 minutes or more and meets 2 of the 3 following criteria (probable migraine**):
- Lasted 4 hours or more
 - Had at least 2 of the following:
 1. Unilateral location
 2. Pulsating quality
 3. Moderate or severe pain intensity
 4. Aggravation by or causing avoidance of routine physical activity
 - Had at least 1 of the following:
 1. Nausea and/ or vomiting
 2. Photophobia and phonophobia
4. Or a day with a headache that is successfully treated with a triptan, ergotamine, or other migraine-specific acute medication CCI

If a headache lasts ≥ 72 hours, the days will still be counted as *headache days* or *migraine days* as aligned with the IHS guidelines.

A day where the symptoms are not recorded for an ongoing headache (missed data entry) will be classified as a headache day.

Further details on the definitions:

CCI

CCI [Redacted]

CCI [Redacted]

4.6.3 Headache Day

A Headache Day is defined as a day with a headache that lasts ≥ 30 minutes or that meets the definition of a Migraine Day (see section 4.6.2).

4.6.4 CCI [Redacted]

CCI [Redacted]

4.6.5 CCI [Redacted]

CCI [Redacted]

4.6.6 CCI [Redacted]

CCI [Redacted]

- [Redacted]
- [Redacted]
- [Redacted]

5 Analysis Sets

The following analysis sets will be used to analyse and present the data:

- *all-participants-enrolled set* (APES) – all screened participants
- *all-participants-randomized set* (APRS) – all randomized participants
- *all-participants-treated set* (APTS) – all participants in the APRS who received an infusion of IMP
- *full-analysis set* (FAS) – all participants in the APTS who have a valid baseline assessment of the number of MMDs and a valid assessment of MMDs over Weeks 1 to 4.
- *full-analysis set long term* (FAS-LT) – all participants in the APTS who have a valid baseline assessment of the number of MMDs and at least one valid post-baseline assessment of MMDs (Weeks 1 to 4 or Weeks 5 to 8 or Weeks 9 to 12)

The participants and data will be classified into the analysis sets according to these definitions at a *Classification Meeting* held after the trial database has been released, but before the blind has been broken.

The presentation and analyses of the primary endpoint, the secondary endpoint (50% MMD response) and safety tables (including exposure, concomitant medications and immunogenicity) will be based on APTS (see section 21.3).

CCI

6 Descriptive Statistics

Unless otherwise specified, summary statistics (n, arithmetic mean, standard deviation [SD], median, lower and upper quartiles, minimum and maximum values) will be presented for continuous variables, and counts and, if relevant, percentages will be presented for categorical variables.

Unless otherwise specified, data listings include site, treatment group, participant screening number, sex, age, race, baseline weight, BMI and CCI

7 Participant Disposition

7.1 Summary of Participant Disposition

Participant disposition will be summarized by treatment group and include the number of participants in each analysis set defined in section 5, and the number of participants in the APTS who completed or withdrew from trial.

If any visits are changed from clinic to remote, a table will be provided presenting by type of visit (on clinic or remote) and treatment group.

7.2 Withdrawals

The number of participants who withdraw from the trial will be summarized by treatment group. The primary reason for withdrawal will be presented, as well as all reasons for withdrawal.

Participants who withdrew from the trial will be listed and the listing will include the number of days in the trial until withdrawal from the trial, the number of days on IMP, the primary reason for withdrawal, all reasons for withdrawal, and a flag if the drug code was broken.

Kaplan-Meier failure plots of time to withdrawal will be presented by treatment group. The time will be calculated from the date of IMP to the date of withdrawal in the Treatment Period. Participants who complete the Treatment Period will be regarded as censored at the End of Week 4 visit (Visit 4).

All tables, graphs, and listings will be based on the APTS.

8 Demographics and Baseline Characteristics

Demographics (sex, age, age group, race and region); baseline characteristics (height, weight, and BMI); baseline disease characteristics; and baseline efficacy variables will be summarized by treatment group.

All the demographics and baseline characteristics data described below will be summarized based on the APTS.

The baseline disease characteristics comprise of:

- age and age group (≤ 21 years, > 21 years) at first diagnosis of migraine
- time since first migraine ICHD-3 diagnosis (years)
- time since first migraine diagnosis group (≤ 15 years, > 15 years)
- current type of migraine (CM or EM)
- time since current migraine ICHD-3 diagnosis (years)
- CCI

o CCI [REDACTED]

- has an MOH diagnosis (yes/no)
- for women: whether migraines started before or after menarche
- for men: whether migraines started before or after puberty
- whether the start of migraine was related to any event

The eDiary reported baseline headache and migraine characteristics (data collected on daily basis during the screening period) that will be summarized are:

- number of baseline MMDs
- number of baseline MHDs

CCI [REDACTED]

CCI [REDACTED]

CCI [REDACTED]

Concurrent as well as relevant past medical, neurological, and psychiatric disorders will be coded using the MedDRA, Version 25.0 (or later) and summarized by treatment group.

A concurrent medical, neurological, or psychiatric disorder is a disorder that is ongoing at the Screening Visit. A past medical, neurological, or psychiatric disorder is a disorder that ended prior to the Screening Visit. Social history will be summarized by treatment group.

Summaries of prior preventive treatment failure medications within 10 years prior to the Screening Visit will be presented by treatment group. The number and percentage of participants with each type of prior treatment failure (lack of efficacy, safety/tolerability, or contraindication) will also be presented by treatment group, as well as the number of prior preventive treatment failures.

9 Recent and Concomitant Medication

Recent and concomitant medication will be coded using the *WHO Drug Dictionary* (WHO-DDE, version March 2022 or later).

Medications will be classified according to the start and stop time and summarized by anatomical therapeutic chemical (ATC) code, generic drug name and treatment group. Handling of missing or incomplete dates is specified in section [22.3.4](#).

The following categories will be used:

- Prior medications: Medications with a stop date before IMP infusion
- Concomitant medication: continued after IMP infusion or started at or after IMP infusion

The tables for prior and concomitant medications will be based on the APTS.

CCI [Redacted]

All disallowed medications entered in the eCRF, which will be identified via a clinical review of the coded medication data in the eCRF, will be listed based on the APRS. The listing will include the generic drug name, the duration, the start and end dates, and dosing information.

CCI [Redacted]

[Redacted]	[Redacted]	[Redacted]	[Redacted]
[Redacted]	[Redacted]	[Redacted]	[Redacted]
[Redacted]	[Redacted]	[Redacted]	[Redacted]
[Redacted]	[Redacted]	[Redacted]	[Redacted]
[Redacted]	[Redacted]	[Redacted]	[Redacted]
[Redacted]	[Redacted]	[Redacted]	[Redacted]
[Redacted]	[Redacted]	[Redacted]	[Redacted]
[Redacted]	[Redacted]	[Redacted]	[Redacted]

[Redacted]

10 Exposure

For the IMP Visit, information related to infusion completed as planned in full (yes/no), infusion temporarily interrupted (yes/no), and infusion lasted longer than 30 (+15) minutes (yes/no), as well as descriptive statistics for the duration of infusion (this duration includes duration of any infusion interruptions), and duration of temporary interruptions will be summarized by actual treatment group.

The summaries will be based on the APTS. All infusion data will be listed.

11 CCI [REDACTED]

[REDACTED]

[REDACTED]

[REDACTED]

[REDACTED]

12 Efficacy

12.1 General Efficacy Analysis Methodology

For the primary and the secondary endpoint concerning MMDs, the efficacy analyses will be based on the APTS. The analyses of the remaining efficacy endpoints with a single post-baseline timepoint will be based on the FAS, while the efficacy endpoints with multiple post-baseline timepoints will be based on the FAS-LT.

All the tables and graphs will be presented by treatment group.

For primary and secondary endpoints, statistical tests for comparisons of the CCI [REDACTED] and CCI [REDACTED] dose of Lu AG09222 versus placebo, will be reported with one-sided p-values and two-sided 90% confidence intervals.

In addition to the above, for primary, secondary, and all exploratory efficacy endpoints, two-sided 95% confidence intervals and p-values for the comparisons of the CCI [REDACTED] and CCI [REDACTED] dose of Lu AG09222 *versus* placebo will be reported.

All two-sided p-values are considered descriptive p-values.

The derivation of the endpoints is described in section 22.1.

12.2 Testing Strategy

The type 1 error will only be controlled for the primary analysis comparing the primary endpoint (the change from baseline in MMDs [Weeks 1 to 4]) for the CCI Lu AG09222 dose versus placebo at a one-sided 5% significance level. Other analyses will be considered exploratory, and statistical significance will be considered indicative rather than confirmative for the finding.

12.3 Analysis Methodology for the Primary Endpoint

12.3.1 Primary Estimand

The primary estimand is the effect of Lu AG09222 that would be seen regardless of whether treatment was administered per protocol and if no preventive migraine therapy was used.

The following intercurrent events (ICEs) will be addressed:

- Use of acute migraine-specific medication
- Use of preventive migraine therapy
- Use of non-migraine specific medication
- IMP not administered per protocol
- COVID-19 Vaccination during the Treatment Period – Treatment Policy Strategy

The attributes of the primary estimand are:

- The **treatment** condition of interest is the comparison of CCI Lu AG09222 to placebo without use of preventive migraine medication.
- The **population** of interest are participants with a diagnosis of migraine, with migraine occurring on CCI per month and headache occurring on ≤ 26 days.
- The **endpoint** to be considered is the change from baseline in MMDs (Weeks 1-4)
- The **population level summary** will be mean difference in the primary endpoint, comparing the effect of CCI Lu AG09222 to placebo.

Intercurrent events:

- use of acute migraine-specific medication implicitly a composite strategy is applied since the definition of the MMDs based on the ICHD-3 guideline includes the impact of the use of acute migraine-specific medication on whether a day is considered a migraine day
- use of acute non-migraine specific medication, that is reported to have successfully treated the headache will be addressed using a treatment policy strategy.
- use of preventive migraine therapy will be addressed using a hypothetical strategy, where data collected after preventive medication intake is considered missing and are handled using missing data analysis methods (see section 22.1.3)
- infusion interruptions or termination before full dose is received will be addressed using a treatment policy strategy.

12.3.2 Strategies for Addressing Intercurrent Events in Primary Estimand

Use of Acute Migraine-Specific Medication – Composite Strategy

A composite strategy will be applied to address the use of acute medication: if acute migraine-specific medication (CCI [REDACTED]) is used during a day, and is reported to have successfully treated the headache, this day counts as a migraine day. See section 4.6.2 for the definitions of a Migraine Day during the Screening Period. The same definitions will be used for the Treatment Period. The eDiary data collected are used regardless of these intercurrent events.

For presentation of this intercurrent event, see section 9.

Use of Preventive Migraine Treatment – Hypothetical Strategy

A hypothetical strategy will be applied to address the use of preventive migraine treatment by setting the eDiary data collected after the use of preventive medication as missing and applying multiple imputation where, for the missing observations, information is borrowed from non-missing observations from the same treatment group.

For presentation of this intercurrent event, see section 9.

Use of Non-migraine Specific Medication – Treatment Policy Strategy

A treatment policy strategy is used to address the intercurrent event of use non-migraine specific medication, that is reported to have successfully treated the headache in which the eDiary data collected are used regardless of these intercurrent events.

IMP not Administered per Protocol – Treatment Policy Strategy

Infusions not completed as planned, infusions temporarily interrupted, and infusions that lasted longer than 30 (+15) minutes could impact the efficacy. These intercurrent events will be addressed using a treatment policy strategy, in which the eDiary data collected are used regardless of these intercurrent events.

For presentation of these intercurrent events, see section 10.

COVID-19 Vaccination During the Treatment Period – Treatment Policy Strategy

A treatment policy strategy is used to address the intercurrent event of getting COVID-19 vaccination during the Treatment Period, in which the eDiary data collected are used regardless of these intercurrent events.

12.3.3 Primary Analysis of the Primary Endpoint

The main estimator for the primary estimand is defined as the least squares mean difference for the mean change from baseline in the number of MMDs over Weeks 1 to 4 between

CCI Lu AG09222 *versus* the placebo group, obtained from an ANCOVA with baseline MMDs as a covariate and treatment (placebo, CCI Lu AG09222, CCI Lu AG09222), population (EM, CM), and CCI

Missing data for the MMD over Weeks 1 to 4 (CCI) will be addressed by using Multiple Imputation performed in which the remaining missing data will be imputed using a sequential regression-based multiple imputation method, based on the imputation models established from the corresponding randomized treatment group.¹

200 simulations will be performed to generate the datasets that will be analysed using the specified ANCOVA model above. These analyses will be combined using Rubin's rule to form a unique point estimate and standard error, taking into account the uncertainty of the imputation.² The combined least square means difference between CCI Lu AG09222 and the placebo group will be evaluated at a one-sided 5% significance level and constitutes the primary analysis.

The SAS[®] code for this analysis is shown in [Appendix IV](#).

The analysis will be performed for the first month of the trial, derived as specified in section [22.1.1](#). The term "month" refers to 4-week periods.

This analysis will include all participants in the APTS.

12.3.4 Rationale for Selected Analysis Method for the Primary Endpoint

The MMDs are considered continuous data, and they are analysed using methods based on observations following a normal distribution. An ANCOVA analysis has been chosen for the primary analysis. Covariates are included in the model based on an approach that includes key factors to represent trial design, namely treatment group, CCI baseline MMD and migraine population (EM, CM) to adjust for baseline differences in disease characteristics.

12.3.5 Sensitivity Analyses of the Primary Endpoint

The following sensitivity analyses will be conducted on the APTS:

- CCI
- Assessing the impact of missing data using placebo-based multiple imputation (pMI): An analysis will be performed using pattern-mixture model (PMM), in which the CCI missing data CCI will be imputed using a regression-based multiple imputation method, based

on the imputation models established from the placebo group. 200 simulations will be performed to generate the datasets that will be analysed using the model described in section 12.3.3. These analyses will be combined using Rubin's rule to form a unique point estimate and standard error, taking into account the uncertainty of the imputation. The SAS® code for this sensitivity analysis is shown in Appendix IV.

12.3.6 CCI [REDACTED]

[REDACTED]

[REDACTED]

[REDACTED]	[REDACTED]

[REDACTED]

[REDACTED]

12.4 Analysis Methodology for the Secondary Endpoints

The following endpoints will be analysed:

- 50% MMD response: $\geq 50\%$ reduction from baseline in MMDs (Weeks 1 to 4)
- change from baseline in the number of MHDs (Weeks 1 to 4)

For 50% MMD response, the estimand strategy will be the same as for the primary analysis (see section 12.3.1), except that the population level summary will be the odds ratio comparing Lu AG09222 CCI and Lu AG09222 CCI to placebo from a logistic regression model with baseline MMDs as covariate and treatment, population (EM, CM), CCI as fixed factor.

The logistic regression model will be fitted using the ML method and the logit link function. In case of convergence issues, the Firth's bias-reducing penalized likelihood method will be applied.

The 200 simulated datasets from the primary analyses (section 12.3.3) will be dichotomized into responders ($\geq 50\%$ reduction of MMDs) and non-responders. Each of the dichotomized datasets will be analysed using the logistic regression model specified above. For each analysis the results will then be transformed into a test statistic, which is approximately standard normally distributed under the null hypothesis of no treatment effect, following the approach by Ratitch et al.,³ The transformed statistics will be combined across the 200 data sets, using PROC MIANALYZE to generate a combined set of estimates, test statistics and p-value for these tests. The SAS[®] code for this analysis is shown in Appendix IV.

The combined odds ratios for Lu AG09222 CCI and CCI compared to placebo will be presented with one-sided p-values and 90% CIs. In addition, the differences in the combined response rates for Lu AG09222 CCI and CCI versus placebo will be presented.

The analysis will be based on the APTS.

For the secondary endpoint, change from baseline in the number of MHDs (Weeks 1 to 4), the estimand strategy will be the same as for the primary analysis (see section 12.3.1).

The endpoint will be analysed with an ANCOVA with baseline MHDs as a covariate and treatment (placebo, CCI Lu AG09222, CCI Lu AG09222), population (EM, CM), CCI as fixed factor.

The analysis will be based on the FAS.

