16.2 Analysis Sets

The following analysis sets will be used for the analyses:

- All patients enrolled set (APES) – all enrolled patients
- All patients randomized set (APRS) – all randomized patients
- All patients treated set (APTS) – all patients in the APRS who received an infusion of IMP
- Full analysis set (FAS) – all patients in the APTS who have a valid baseline assessment of the number of MMDs and a valid assessment of the number of MMDs over Weeks 1 to 4
- Full analysis set long term (FAS-LT) – all patients in the APTS who have a valid baseline assessment of the number of MMDs and at least one valid post-baseline assessment of MMDs (Weeks 1 to 4 or Weeks 5 to 8 or Weeks 9 to 12)
- CCI

The patients and data will be classified into the analysis sets according to these definitions at a *Classification Meeting* held after the study database has been released, but before the blind has been broken.

Safety will be reported based on the APTS. Efficacy in the treatment period will be reported for the FAS. Maintenance of effect covering efficacy in the treatment period as well as the safety follow-up period will be reported for the FAS-LT.

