16.8.5 Analysis of the Secondary Endpoints

For the secondary endpoints based on response rates, the estimand strategy will be the same as for the primary analysis, except that the population level summary will be the odds ratio comparing Lu AG09222 to placebo from a logistic regression model with baseline MMDs as covariate, treatment as a fixed factor, and population (EM or CM) and CCI

In general, endpoints based on a change from baseline to Weeks 1 to 4 or to Week 4 will be analysed following the approach for the primary endpoint. For endpoints related to MMD or monthly headache day, the IE “Use of acute rescue medication” will be addressed using a composite strategy. For other endpoints, a treatment policy approach will be used for this IE.

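### Change in MHDs (Weeks 1 to 4) shares the primary estimand strategy but is analysed on the FAS, dropping treated participants whom both MMD endpoints keep by imputation

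*SAP*

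**What the plan says.** For MHD, SAP 12.4 states: "For the secondary endpoint, change from baseline in the number of MHDs (Weeks 1 to 4), the estimand strategy will be the same". The comparator is the primary analysis, and the reference given is 12.3.1. Under that strategy, "data collected after preventive medication intake is considered missing and are handled using missing data analysis methods". SAP 12.3.2 names the method as multiple imputation borrowing from the same treatment group, and 12.3.3 applies it to the whole APTS with 200 datasets. SAP 22.1.3 repeats that data after preventive intake are set to missing.

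The analysis sets then diverge:

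- **Primary endpoint and 50% MMD response.** SAP 12.1: "For the primary and the secondary endpoint concerning MMDs, the efficacy analyses will be based on the APTS". For 50% response, 12.4 reuses the 200 imputed datasets and adds "The analysis will be based on the APTS".
- **MHD.** SAP 12.4 specifies an ANCOVA with baseline MHDs as covariate, states no imputation step, and ends "The analysis will be based on the FAS".
- **FAS entry.** SAP 5 requires "a valid baseline assessment of the number of MMDs and a valid assessment of MMDs over Weeks 1 to 4". The condition is on MMDs, not MHDs.

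The protocol had one set for all of this. Section 16.2: "Efficacy in the treatment period will be reported for the FAS". The SAP moved only the two MMD endpoints to the APTS.

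**The concern.** Three Weeks 1 to 4 endpoints come from the same diary and share a stated estimand strategy, yet one of them rests on a different group of participants, selected after randomisation by another endpoint's validity.

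The participants lost are partly those for whom the strategy was written. Someone who starts a preventive early in the month has the later diary data set to missing and may have no valid month. For the MMD endpoints that person is imputed; for MHD that person is removed.

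The filter is also keyed to the wrong variable. Under SAP 22.1.1.1, a day with a headache of at least 30 minutes is a headache day, even though missing headache characteristics can make it a missing observation for migraine day. A participant can therefore have usable MHD data and still fail FAS entry on MMDs.

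At stake is the comparability of a secondary result with the primary one. Bias arises if exclusion rates differ between arms, or if excluded participants differ from included ones by different amounts in each arm.

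**Working it through.** **1. The plan's own figure.** Inputs from SAP 19: effect 2.1 days, one-sided 5%, power 80%, SDs 3.8 (30% EM) and 6.1 (70% CM).
- Within-population SD = √(0.3 × 3.8² + 0.7 × 6.1²) = √30.38 = 5.51.
- n per arm = 2 × (1.645 + 0.842)² × SD² / 2.1². With SD 5.51 this is 85.2, so 86, which reproduces the SAP. With the stated overall SD of 5.6 it is 87.9, so 88.
- Dropout: 43 / 0.95 = 45.3, so 46; the 2:1:2 ratio then gives 92:46:92 = 230.

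No figure is in dispute. These inputs only set the scale, because the documents give no effect or SD for MHD.

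**2. Who loses the month.** Protocol 16.8.2 sets a 28-day value to missing at 13 or fewer recorded days and prorates at 14 or more. Assume an otherwise complete diary with data after intake removed:
- preventive start on day 13 or earlier: month missing, participant outside the FAS;
- day 14: depends on whether the intake day is kept;
- day 15 or later: at least 14 days remain, so the month is prorated and kept.

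Others at risk are those who withdraw consent early and those who stop recording.

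**3. How many.** If all of the planned 5% withdrawals lost the month: 0.05 × 92 = 4.6, 0.05 × 46 = 2.3 and 0.05 × 92 = 4.6, in total 11.5 of 230. If half did: 5.75. If none did: 0. Preventives are disallowed (protocol Appendix II), and withdrawn participants other than consent withdrawers continue the diary to Week 4 (protocol 8.9), so the lower part of the range is more plausible.

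**4. Bias from analysing included participants only.** Let p be the excluded share and D the mean change in excluded minus included participants; subscript 1 is active and 0 is placebo. Bias in the active-minus-placebo difference = −(p₁D₁ − p₀D₀). All values of p and D below are assumptions.

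| p₁ v p₀ | D₁ v D₀ (days) | Bias (days) |
|---|---|---|
| 5% v 5% | 3 v 3 | 0 |
| 1% v 1% | 3 v 0 | −0.03 |
| 5% v 5% | 3 v 0 | −0.15 |
| 8% v 2% | 3 v 3 | −0.18 |

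Negative values flatter the active arm. A bias of 0.4 days at 8% v 2% needs a gap of 0.4 / 0.06 = 6.7 days in both arms, which is strongly informative loss. For comparison, the SE is about 5.51 × √(2/87.4) = 0.83 to 5.6 × √(2/87.4) = 0.85, so about 0.84.

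**5. Does imputation help?** Simulation: 400 runs per case, arms 92/46/92, 30% EM, 200 within-arm imputations. Assumed: baseline means 11 (EM) and 20 (CM), the plan's MMD SDs and effect as stand-ins for MHD.
- Imputing from baseline only, against complete-case ANCOVA: mean absolute difference 0.012, 0.021 and 0.034 days at 2.5%, 5% and 10% missing.
- Informative loss, 8% v 2%, excluded participants about 3.5 days worse: bias −0.21 for complete-case ANCOVA and −0.21 for baseline-only imputation. With a later diary month as predictor (assumed correlation 0.7) it is −0.12. That predictor is often unavailable, because data after preventive use are set to missing and a withdrawn participant's diary closes at Week 4.
- Strongly informative loss, 8% v 2%, bias about 0.4 days: adding the days already recorded in Weeks 1 to 4 as predictor removed nearly all of it and recovered some precision. This requires that the recorded days largely explain who is lost; where loss depends on the unrecorded days, the correction is only partial.

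**The case against.** The best defence is that the split is intended. SAP 12.1 states it as a general rule, and SAP 5 and 12.4 follow it. That stands: this is not a drafting slip.

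A reader might infer a breach of protocol 16.8.5, whose rule for such endpoints reads: "change from baseline to Weeks 1 to 4 or to Week 4 will be analysed following the approach for the primary endpoint". The documents do not support this. The sentence is qualified as a general rule, and the protocol's own primary approach was ANCOVA on the FAS with prorating (16.2, 16.8.2). MHD stayed with that approach; the MMD endpoints moved.

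A shared estimand strategy also does not force a shared estimator. SAP 12.3.1, the section that 12.4 cites for MHD, names neither multiple imputation nor the APTS. If data are missing at random given the ANCOVA covariates, complete-case ANCOVA targets nearly the same quantity, and step 5 confirms that baseline-only imputation gains essentially nothing. This also stands, and it narrows the fix to one that uses partial-month data.

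Redaction limits what can be said. SAP 21.3 may give the reason for the split. Most of the MMD derivation in 22.1.1.2 is hidden, so the 13-day cut-off is known only from the protocol. The imputation code is hidden too, so the programming effort and the predictors used for MMDs cannot be checked. A missing rationale is therefore no part of this point. But the visible text fixes MHD on the FAS, and hidden code cannot return participants whom that set excludes.

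**Conclusion.** The point holds as a minor misalignment of estimand strategy, analysis set and estimator for one secondary endpoint. Treated participants without a valid Weeks 1 to 4 MMD are imputed for two endpoints and dropped for the third, and the filter tests MMD and not MHD validity.

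The effect is small and rests on assumptions: 0 to about 12 participants of 230, and a bias between 0 and roughly 0.2 to 0.4 days, the upper end only with unequal and informative loss that the documents give no reason to expect. MHD is outside type 1 error control (SAP 12.2).

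Two stronger readings should be resisted. The MHD result is not shown to be materially biased. Nor would imputation as such repair it: the gain beyond alignment depends on using the recorded part of the month.

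**What to change.** In SAP 12.4, with matching wording in 5 and 12.1:

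- Analyse MHD on the APTS with within-arm multiple imputation of the 12.3.3 type. Include as predictor the participant's recorded Weeks 1 to 4 headache days before any preventive intake. Then apply the stated ANCOVA and Rubin's rule.
- Keep the complete-case ANCOVA as supportive, on a set defined by valid baseline and Weeks 1 to 4 MHD.
- State whether the MMD imputation uses the same kind of predictor, so that any difference between the models is visible.

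If the FAS is kept as the main set, one sentence saying that MHD is analysed without imputation, and why (unless redacted 21.3 already does so), would make the difference explicit.

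The cost is SAP wording, added programming for the imputation model, and one further set of output.
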